Monitoring and Management Plans for Triglyceride Elevations:

Elevated Triglycerides:

Patients may continue to use stable doses of TG-lowering medications during the study. An adjunctive therapy plan is in place for those patients whose TG values meet the protocol-defined threshold criteria. Post-randomization, TG results will be masked to investigators in order to maintain the blind; however, a threshold has been set to notify investigators and provide an opportunity to adjust the patient's standard of care regimen. Beginning at Week 4 (Visit T2), if the TG level exceeds 1000 mg/dL (11.3 mmol/L) while on treatment, the investigator will receive notification from the central laboratory that the patient has met or exceeded the protocol-defined threshold criteria for TG. The investigator will initiate the following plan:

- Any patient with TG >1000 mg/dL (11.3 mmol/L) will be reminded to fast for at least 10 hours and will return to clinic within 1 week for a repeat, fasting TG sample to confirm the TG value

meets the threshold criteria

- Any patient with a confirmed TG >1000 mg/dL (11.3 mmol/L) may initiate standard-of-care therapy (however, gemfibrozil may not be added) to lower TG using a patient-specific prescription. The initiation of this medication will be documented on the case report form as a concomitant medication with the associated start date. These medications will not be provided by the sponsor.
- Patients continuing to exceed the TG threshold after maximizing the standard-of-care triglyceride-lowering therapy will be discontinued from investigational medicinal product (IMP) treatment and will be asked to continue to be followed for safety using the protocol-specified visit schedule.

Monitoring and Management of Potential AEs and Adverse Events of Special Interest (AESI)

Potential AEs:

Based on findings in nonclinical models, potential AEs include reversible hypoglycemia and metabolic acidosis. Potential cases of reversible hypoglycemia and metabolic acidosis will be identified by routine safety monitoring of AEs and clinical safety laboratories.

Musculoskeletal Safety:

Patients with CK abnormalities will also be reviewed for any other lab changes, such as creatinine, and any reported AEs or SAEs. Musculoskeletal events will be identified and evaluated by routine safety monitoring of PE findings and AEs.

Hepatic:

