Post-randomization values for individual laboratory measures for LDL-C, TG, TC, HDL-C, non-HDL, apoB, and hs-CRP, including any plasma concentration of bempedoic acid and its metabolite that may inadvertently suggest treatment assignment will not be available to personnel from the clinical site, the patient, the Sponsor, and CRO.

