8.4. Early Withdrawal from Study or Treatment

Patients who withdraw from study drug prior to Week 24 (Visit T5) for any reason will be asked to continue to be followed for safety assessments, including basic fasting lipids, at clinic visit following the protocol-specified visit schedule (see [Section 8.3](#)).

Patients who temporarily withdraw from study drug prior to Week 24 (Visit T5) for any reason may restart study drug providing that 1) the patient and the investigator are in agreement regarding this course of action, 2) the patient has been off of study drug for 4 weeks or less; and 3) study drug can be started as soon as possible. For cases where the patient has been off of study drug for more than 4 weeks, the investigator must contact the medical monitor for approval prior to restarting study drug.

Patients who do not wish to continue to return to the clinic for safety assessments will be asked to participate in phone calls from the site at protocol-specified visits (see [Section 8.3](#)), or at a minimum at 24 weeks, to collect information on AEs, concomitant medications, and current health status.

The patient's decision to participate in the clinical study is voluntary. Patients may refuse to continue in the study and/or withdraw from participation in this study at any time, for any reason, specified or unspecified, and without penalty or loss of benefits to which the patient is otherwise entitled.

It is the right and duty of the Investigator to interrupt the treatment of any patient whose health or well-being may be threatened by continuation in this study. Such patients should be withdrawn from the study and should not be continued under a modified regimen.

Patients who are withdrawn from the study may not re-enter. The reasons for withdrawal from this study or treatment may include:

- Patient's withdrawal of consent
- Failure to comply with the protocol
- Lost to follow-up
- Illness, condition, or procedural complication (including AEs) affecting the patient's ability to participate or requiring prohibited medication
- The Sponsor or Investigator terminates the study
- In the Investigator's judgment, it is deemed in the best interest of the patient to discontinue his/her participation in the study
- Any other reason

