8.4.1. Procedures for Early Withdrawal

If a patient withdraws or is removed from the study for any reason, all "End of Study" procedures should be completed. Reason for withdrawal, date of the discontinuation, and date of the last dose of study drug should be recorded in the appropriate section of the eCRF.

Additionally, the discontinuation visit date must be registered in IWRS. Study drug assigned to the withdrawn patient may not be assigned to another patient.

All effort should be made to have each patient complete all study visits on schedule according to the protocol. Accommodations for early or late visits in special circumstances will be considered by the Sponsor to prevent early withdrawal. Written notice (regardless of cause) is to be provided within 48 hours of the withdrawal to the Sponsor personnel or the Medical Monitor. At the time of discontinuation, every effort should be made to ensure all relevant procedures and evaluations scheduled for the final study visit are performed.

Patients choosing to withdraw from the study early should be encouraged to return for all study scheduled clinic visits even if they are no longer taking IMP. Patients who withdraw from all aspects of the study will be asked to consent to clinical visits or phone calls for safety assessments, including AEs, concomitant medication, and current health status through Week 24 (Visit T5). Subjects who are unwilling to return for clinic visits should return for an end of study visit (Visit T5).

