10.2.12. Monitoring and Management of Elevated Triglycerides

Patients may continue to use stable doses of TG-lowering medications during the study. An adjunctive therapy plan is in place for those patients whose TG values meet the protocol-defined threshold criteria. Post-randomization, TG results will be masked to investigators in order to maintain the blind; however, a threshold has been set to notify investigators and provide an opportunity to adjust the patient's standard of care regimen. Beginning at Week 4 (Visit T2), if the TG level exceeds >1000 mg/dL (11.3 mmol/L) while on treatment, the investigator will receive notification from the central laboratory that the patient has met or exceeded the protocol-defined threshold criteria for TG. The investigator will initiate the following plan:

- Any patient with TG >1000 mg/dL (11.3 mmol/L), will be reminded to fast for at least 10 hours and will return to clinic within 1 week for a repeat, fasting TG sample to confirm the TG value meets the threshold criteria
- Any patient with a confirmed TG >1000 mg/dL (11.3 mmol/L) may initiate standard-of-care therapy to lower TG using a patient-specific prescription. The initiation of this medication will be documented on the case report form as a concomitant medication with the associated start date. These medications will not be provided by the sponsor.
- Patients continuing to exceed the TG threshold after maximizing the standard-of-care triglyceride-lowering therapy will be discontinued from study drug treatment and will be asked to continue to be followed for safety using the protocol-specified visit schedule (see [Section 8.3](#)).
- Please see the Clinical Laboratory Manual for sample collection and instructions.

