11.5. Primary Endpoint Analysis

The primary efficacy endpoint is the percent change from baseline to Week 12 in LDL-C. Baseline is defined as the mean of the values from Week -1 (Visit S3) and predose Day 1/Week 0 (Visit T1).

The primary efficacy endpoint will be analyzed using analysis of covariance (ANCOVA), with treatment group and patient type (primary prevention; secondary prevention) as factors and

baseline LDL-C as a covariate. The ANCOVA will be performed using the FAS, with patients included in their randomized treatment group regardless of the treatment they actually received. The details of the ANCOVA model and options to account for unequal variances and group size will be described in the SAP.

Missing data for the primary endpoint will be imputed using a multiple imputation method that accounts for treatment adherence. A pattern mixture model (PMM) will be used to specify different imputation strategies depending on whether the patient is still on study treatment. Patients with missing LDL-C data at Week 12 who are no longer taking study treatment can be assumed no longer to be benefitting from study medication, and their missing value(s) can be assumed to be similar to those from placebo patients. In this instance, it is reasonable to impute LDL-C values in a model including placebo patients' data only. Patients with missing LDL-C data at Week 12 who are still taking study treatment can be assumed to continue to benefit from study medication, and their missing value(s) can be assumed to be similar to those who remain on study treatment and have data. In this instance, it is reasonable to impute LDL-C values based on the observed values in their randomized treatment group at Week 12. Details for the PMM will be described in the SAP.

To account for uncertainty, missing values will be imputed using multiple imputation. Imputed datasets will be analyzed using an ANCOVA model with the treatment and patient type (primary prevention; secondary prevention) as factors and baseline LDL-C as a covariate. Approximately 200 imputed datasets will be created, with results from the analysis of each imputed dataset combined using Rubin's method. For each type of ANCOVA (observed case; imputation via PMM), the least squares mean (LSM) and standard error (SE) will be provided for both treatment groups, along with the placebo-corrected LSM, its 95% confidence interval (CI) and associated p-value.

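### The only alert for triglycerides above 1000 mg/dL is limited to patients on treatment, so a masked elevation in a patient followed off drug has no stated route to the investigator

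*Protocol*

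**What the plan says.** **Masking.** Protocol Section 6.3 lists "Post-randomization values for individual laboratory measures for LDL-C, TG, TC, HDL-C, non-HDL, apoB, and hs-CRP" among the results withheld from the site, the patient, the Sponsor and the CRO. The Synopsis and Section 10.2.12 also say that TG is masked to investigators after randomization. None of the three makes an exception for patients who have stopped drug.

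**The alert.** The Synopsis provides that, beginning at Week 4, "if the TG level exceeds 1000 mg/dL (11.3 mmol/L) while on treatment, the investigator will receive notification from the central laboratory". Section 10.2.12 repeats the limit: "while on treatment, the investigator will receive notification from the central laboratory". Three steps follow: a repeat fasting sample within a week, standard-of-care TG-lowering therapy if the value is confirmed, and discontinuation of study drug if TG stays above the threshold on maximal therapy.

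**Follow-up off drug.** Under Section 8.4, patients who stop drug early "will be asked to continue to be followed for safety assessments, including basic fasting lipids", on the normal visit schedule. Section 8.4.1 adds that those who withdraw early "should be encouraged to return for all study scheduled clinic visits even if they are no longer taking IMP". The note to Table 2 in Section 8.3 drops only apoB and hs-CRP for these patients, and footnote 11 lists triglycerides in the basic lipid panel. Attendance is voluntary: "Patients who do not wish to continue to return to the clinic for safety assessments will be asked to participate in phone calls".

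**The concern.** Masking TG protects the blind, and the 1000 mg/dL alert is the safeguard that makes the masking acceptable. The masking covers all patients, but the alert as worded may cover only those taking study drug. A patient who stopped drug for, say, a liver-enzyme elevation, and who keeps attending, would have TG drawn as a safety measure. The result would be withheld, and nothing in the protocol would tell the site that it had crossed the protocol's own action threshold. The stake is the safety of a few individual patients. The primary endpoint, type I error and power are not affected.

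Patients taken off drug because of persistently high TG are outside this concern, since the site already knows about them.

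**Working it through.** The plan gives no figure to reproduce, so the check is mainly of the text, followed by a bound on size.

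**1. Does any other stated route reach the investigator?**
- Section 10.1.6.4 has the investigator review laboratory results as they become available. Section 6.3 makes TG unavailable, so this does not help.
- The lipid table for the Data Monitoring Committee (SAP Appendix 3, Table 14.3.2.10) is a summary for the committee, not a notification to the site.
- The Clinical Laboratory Manual is cited at the end of Section 10.2.12 for sample collection and instructions. It is not among the documents.

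No stated route was found.

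**2. What does the on-treatment limit mean?**
- The other laboratory triggers apply at any time after randomization: hemoglobin and eGFR (Section 10.2.11.1), ALT/AST (10.2.11.3.2), CK (10.2.11.3.3) and eGFR again (10.2.11.3.5). Only the TG trigger is limited to time on treatment.
- Section 11.5 specifies "different imputation strategies depending on whether the patient is still on study treatment" and contrasts that group with "Patients with missing LDL-C data at Week 12 who are no longer taking study treatment". Being on treatment there means taking drug.
- SAP Section 18.2.3.3 defines the on-treatment period as running to the last dose plus 7 days. SAP Appendix 4 has an on-treatment column in which cohorts 7 and 8 have Week 12 values although they are not on treatment. The sponsor therefore expects lipid results from patients off drug and uses the term for drug-taking.

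**3. How many draws per patient?** Scheduled TG draws from Week 4 are T2 (Day 29), T4 (Day 85) and T5 (Day 169).

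| Drug stopped | Maximum draws without a stated alert |
|---|---|
| Before T2 | 3 |
| Between T2 and T4 | 2 |
| Between T4 and T5 | 1 |

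These are upper bounds. Clinic attendance off drug is voluntary, and a patient who stopped only days before a draw might still count as on treatment.

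**4. How many patients?** The documents give no rate of stopping, of attendance off drug or of TG above 1000 mg/dL, so all three rates below are assumptions.

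Patients affected = 300 × P(stops early) × P(later TG >1000, given stopped) × P(attends off drug)

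| | Stops early | TG >1000 | Attends | Patients |
|---|---|---|---|---|
| Low, full attendance | 0.05 | 0.005 | 1 | 300 × 0.05 × 0.005 × 1 = 0.075 |
| High, full attendance | 0.20 | 0.02 | 1 | 300 × 0.20 × 0.02 × 1 = 1.2 |
| Low, half attend | 0.05 | 0.005 | 0.5 | 300 × 0.05 × 0.005 × 0.5 = 0.0375 |
| High, half attend | 0.20 | 0.02 | 0.5 | 300 × 0.20 × 0.02 × 0.5 = 0.6 |

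The range is about 0.04 to 1.2 patients. Exclusion criterion 1 (TG of 500 mg/dL or more at screening) also points to a low count.

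**The case against.** The strongest reply is that the phrase means the 24-week treatment period, not drug intake.
- The sentence is anchored to a visit, and the protocol's post-randomization visits are titled as treatment weeks (Sections 8.3.5 to 8.3.8). Patients off drug are asked to attend that same schedule.
- Where drug intake is meant, the protocol usually adds a qualifier such as study drug or IMP. The TG trigger has none.
- The first two action steps open with any patient above the threshold.
- On the drug-taking reading, the alert would lapse for patients stopped because of TG, although the plan goes on following them for safety.

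A second reply is practical. The central laboratory issues the alert, and no section describes it being told who has stopped drug. An alert triggered by the value alone, possibly set out in the Clinical Laboratory Manual, is therefore plausible.

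These points show that the wording is ambiguous and that no patient can be shown to be exposed. They do not make the treatment-period reading the better one: the other triggers use broader wording, and the SAP uses the unqualified term for drug-taking. Whatever the laboratory does in practice, the protocol sets a rule that, followed literally, can leave a safety result unreported. It also stands that the patient counts rest wholly on assumed rates and are mostly below one.

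**Conclusion.** The point holds as a minor, conditional one. TG is masked at every post-randomization draw, off-drug draws are planned, and the only stated alert is limited to time on treatment. Read as taking study drug, that limit leaves up to three draws per patient without a stated alert, in roughly 0.04 to 1.2 of 300 patients on assumed rates. Confidence is medium. The gap closes in the protocol text if the treatment-period reading was intended, and in practice if the Laboratory Manual already alerts on every value. The change is optional and worth making because it is cheap.

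**What to change.** In the Synopsis and in Section 10.2.12, replace the on-treatment limit with wording that applies the alert at any post-randomization draw from Week 4 through Week 24, whether or not the patient is still taking IMP. Add one sentence stating that the repeat fasting TG and standard-of-care steps apply to all such patients, and that the IMP-discontinuation step applies only to those still taking it. Set the central-laboratory alert, and the Laboratory Manual if it differs, to match. If the manual already covers patients off drug, only the protocol wording needs aligning.

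The cost is one phrase and one sentence in two places, plus one alert setting. No scheduled draws are added. The downside is a few extra notifications and repeat samples. A notified off-drug patient might also start TG-lowering therapy while still counted in the Full Analysis Set, but at these numbers the effect on the LDL-C comparison is negligible. Each notification tells the site only that the threshold was crossed, as already planned for patients on drug.

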3. ABBREVIATIONS AND DEFINITIONS

Abbreviation	Definition
ACC	American College of Cardiology
ACL	Adenosine triphosphate-citrate lyase
ACS	Acyl-CoA synthetase
ADR	Adverse drug reaction
AE	Adverse event
AESI	Adverse events of special interest
AHA	American Heart Association
ALB	Albumin
ALK-P	Alkaline phosphatase
ALT	Alanine aminotransferase
ANCOVA	Analysis of covariance
apoB	Apolipoprotein B
AST	Aspartate aminotransferase
ATP	Adenosine triphosphate
AUC ₀₋₂₄	Area under the curve during 24 hours
BMI	Body mass index
BP	Blood pressure
BUN	Blood urea nitrogen
Ca	Calcium
CABG	Coronary artery bypass graft
CEC	Clinical Events Committee
CETP	Cholesterol ester transfer protein
CFR	Code of Federal Regulations
CHD	Coronary heart disease
CI	Confidence interval
CK	Creatine kinase
Cl	Chloride
C _{max}	Time to peak maximum concentration
CMV	Cytomegalovirus
CNS	Central nervous system

Abbreviation	Definition
CoA	Acetyl-coenzyme A
CO ₂	Carbon dioxide
CRO	Contract research organization
CTA	Computed tomography angiography
CV	Cardiovascular
CVD	Cardiovascular disease
CYP	Cytochrome P450
DBP	Diastolic blood pressure
DMC	Data Monitoring Committee
EAS	European Atherosclerosis Society
EC	Executive committee
ECG	Electrocardiogram
eCRF	Electronic case report form
eGFR	Estimated glomerular filtration rate
EMA	European Medicines Agency
ESC	European Society of Cardiology
ETC-1002	Bempedoic acid
EU	European Union
FAS	Full analysis set
FDA	US Food and Drug Administration
FSH	Follicle-stimulating hormone
GCP	Good Clinical Practice
GI	Gastrointestinal
HbA _{1C}	Glycosylated hemoglobin, Type A _{1C}
HBsAg	Hepatitis B surface antigen
Hct	Hematocrit
HCV	Hepatitis C virus
HCV-ABV _{ivi}	Hepatitis C antibodies
HDL-C	High-density lipoprotein cholesterol
HeFH	Heterozygous familial hypercholesterolemia
Hgb	Hemoglobin
HMG-CoA	3-hydroxy-3-methylglutaryl coenzyme A

Abbreviation	Definition
hr	Hour
HR	Heart rate
hs-CRP	High-sensitivity C-reactive protein
IB	Investigator's Brochure
ICD	Informed Consent Document
ICH	International Conference on Harmonisation
IEC	Independent Ethics Committee
IMP	Investigational medicinal product
IND	Investigational New Drug Application
INR	International normalized ratio
IRB	Institutional Review Board
ITT	Intention-to-treat
IWRS	Interactive web response system
K	Potassium
LDH	Lactate dehydrogenase
LDL-C	Low-density lipoprotein cholesterol
LDLR	Low-density lipoprotein receptor
LFT	Liver function test
LS	Least squares
LSM	Least squares mean
MACE	Major adverse cardiovascular event
MCH	Mean corpuscular hemoglobin
MCHC	Mean corpuscular hemoglobin concentration
MCV	Mean corpuscular volume
MDRD	Modification of diet in renal disease
MED ID	Medication identification
MedDRA	Medical Dictionary for Regulatory Activities
MI	Myocardial infarction
MRI	Magnetic resonance imaging
Na	Sodium
NA	Not applicable
NLA	National Lipid Association

Abbreviation	Definition
NOAEL	No-observed-adverse-effect level
non-HDL-C	Non-high-density lipoprotein cholesterol
PAD	peripheral arterial disease
PCI	Percutaneous coronary intervention
PCSK9	Proprotein convertase subtilisin/kexin type 9
PE	Physical exam
PK	Pharmacokinetic(s)
PMM	Pattern mixture model
PT	Prothrombin time
RBC	Red blood cell
RNA	Ribonucleic acid
SAE	Serious adverse event
SAP	Statistical Analysis Plan
SBP	Systolic blood pressure
SE	Standard error
SGOT	Serum glutamic oxaloacetic transaminase
SGPT	Serum glutamic pyruvic transaminase
SI	Statin intolerant
siRNA	small interfering ribonucleic acid
SOC	System organ class
SP	Safety population
SUSAR	Suspected and unexpected serious adverse reaction
$t_{1/2}$	Terminal elimination half-life
T2DM	Type 2 diabetes mellitus
TB	Total bilirubin
TC	Total cholesterol
TEAE	Treatment-emergent adverse event
TG	Triglycerides
TIA	Transient ischemic attack
TSH	Thyroid-stimulating hormone
TQT	Thorough QT/QTc
ULN	Upper limit of normal

Abbreviation	Definition
US	United States
WBC	White blood cell
WHO	World Health Organization

4. INTRODUCTION

4.1. Overview of the Disease Under Study

Bempedoic acid (ETC-1002) is an inhibitor of adenosine triphosphate-citrate lyase (ACL) (adenosine triphosphate [ATP] citrate lyase), an enzyme upstream of 3-hydroxy-3-methylglutaryl coenzyme A (HMG-CoA) reductase in the cholesterol biosynthesis pathway. It is an oral first-in-class small molecule designed to lower low-density lipoprotein cholesterol (LDL-C) levels in patients with high cardiovascular risk unable to meet their treatment goals with currently available lipid-lowering therapies.

More people die annually from cardiovascular disease (CVD) than from any other disease. CVD remains the leading cause of death among Europeans, Americans, and other populations around the world (WHO 2015). In the United States (US), based on 2011 data, more than 2,150 Americans die from CVD per day, an average of 1 death every 40 seconds (Mozffarian 2015). The relationship between CVD and elevations in LDL-C is undisputed. Many clinical studies have demonstrated that lowering elevated levels of LDL-C reduces the risk of heart attacks, stroke, and death (Baigent 2010). More than half of the adult population has high cholesterol; therefore, lowering elevated LDL-C is a very important step in the battle against heart disease. It is also known that elevation of high-sensitivity C-reactive protein (hs-CRP; a measure of systemic inflammation) has been associated with increased cardiovascular (CV) risk (Bikdeli 2011; Vidula 2008), and lowering hs-CRP with statin therapy—independent of the level of LDL-C achieved with the statin treatment—significantly reduces recurrent coronary events (Ridker 2005). Given the evidence, hs-CRP is included as a risk indicator in the Reynolds Risk algorithm (Ridker 2007) and in clinical practice guidelines for the management of dyslipidemia (Jacobson 2014; Stone 2013). The Reynolds Risk score, which includes hs-CRP, has proved to be an excellent CV risk assessment tool (DeFilippis 2011).

The use of HMG-CoA reductase inhibitors, or statins, is one of the most important advances in the management of CVD, decreasing CV morbidity and mortality by approximately 25% in eligible patients (Joy 2009). However, tolerability is an important barrier to statin adherence. Muscle complaints, which encompass a range of conditions from myalgia to rare but life-threatening rhabdomyolysis, represent a major cause of statin discontinuation in clinical practice (Joy 2009). In addition, a range of other signs and symptoms may lead to discontinuation, including elevated liver enzymes, gastric upset, diarrhea, constipation, rash, headache, dizziness, mental confusion, forgetfulness, and erectile dysfunction (Eckel 2010). The statin intolerant (SI) patient population constitutes a major public health concern.

Guidelines now recommend very aggressive lowering of LDL-C in high-risk individuals to levels below 100 mg/dL and often under 70 mg/dL (Jacobson 2014) or reduction of $\geq 50\%$ (Stone 2013). Worldwide, statins are used by tens of millions in order to achieve these aggressive lipid goals. Recent guidelines for the treatment of hypercholesterolemia are likely to further increase the number of patients taking statins, possibly to as many as 1 in 3 American adults. Consequently, as the number of statin-treated patients grows, the problem of statin intolerance will increase in importance as a public health concern. Current guidelines recognize that some patients develop intolerable side effects with statins. These guidelines recommend

patients be treated with the maximum-appropriate intensity of a statin that does not cause adverse effects (Stone 2013).

